HEOR	Health Economics, Outcomes & Reimbursement
IBW	Ideal Body Weight
ICH	International Committee on Harmonization
ID	Identifier
INN	International Non-proprietary Name
ITT	Intent-to-treat
IV	Intravenous

IVRS/IWRS	Interactive voice/web response system
IXRS	Interactive response system (independent of type)
JSRC	Joint Safety Review Committee
kBq	Kilobecquerel
LCL	Lower Confidence Limit
LTFU	Long-Term Follow-Up
LTFUAE	Long-Term Follow-Up Adverse Event
MedDRA	Medical Dictionary for Regulatory Activities
MRI	Magnetic resonance imaging
NCI	National Cancer Institute
NCCN	National Comprehensive Cancer Network
NIS	Non-interventional Study
NIST	National Institute of Standards and Technology
nMiss	Number of missing values
OS	Overall survival
PC	Prostate cancer
mPCWG2	Modified Prostate Cancer Working Group 2
PRO	Patient Reported Outcomes
PSA	Prostate specific antigen
PT	Preferred Term
QoL	Quality of Life
Ra-223	Radium-223 dichloride
rPFS	Radiological progression free survival
SAE	Serious Adverse Event
SAF	Safety
SAP	Statistical Analysis Plan
SD	Standard Deviation
SMQ	Standardized MedDRA Queries
SOC	System Organ Class
SOP	Standard Operating Procedure
SSE	Symptomatic skeletal event
SSE-FS	Symptomatic skeletal event free survival
Std	Standard Deviation
TAS	(Bayer) Therapeutic Area (Oncology) Standards
TBW	Total Body Weight
TEAE	Treatment-Emergent Adverse Event
TTP	Time to progression
uCi	Microcurie
UCL	Upper Confidence Limit
W12	Week 12
W24	Week 24
WHO	World Health Organization
WHO-DD	World Health Organization Drug Dictionary

1. Introduction

Protocol 16507 is a 3-arm, randomized, open-label Phase II study to compare the efficacy and safety of a “standard dose” regimen of radium-223 dichloride with, a “high dose” regimen and an “extended dose” regimen, in subjects with castration-resistant prostate cancer metastatic to bone .

The study's 3 arms are:

- Arm A: 6 doses of 50 kBq/kg (55 kBq/kg after implementation of NIST update) radium-223 dichloride every 4 weeks ("standard" dose regimen)
- Arm B: 6 doses of 80 kBq/kg (88 kBq/kg after implementation of NIST update) radium-223 dichloride every 4 weeks ("high dose" regimen)
- Arm C: 12 doses of 50 kBq/kg (55 kBq/kg after implementation of NIST update) radium-223 dichloride every 4 weeks ("extended dose" regimen)

The study's co-primary endpoints are:

- Symptomatic skeletal event free survival from randomization (SSE-FS1) for the "standard dose" vs. "high dose" comparison (Comparison 1).

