3.2 Schedule of procedures

See Protocol Table 7-1.

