Progressive Disease (PD)	Two or more new areas of radiotracer uptake attributable to metastatic disease in regions of bone that had not previously shown radiotracer uptake or greater than 30% increase from baseline in bone scan lesion area in areas attributable to metastatic disease.
Unable to Evaluate (UE)	Assigned if bone scan results cannot be interpreted due to inconsistent image acquisition parameters compared to the reference scan, incomplete imaging, or other similar technical deficiencies.

Subjects with no randomization baseline assessment or a baseline BSLA value of 0 will be assigned ‘UE’ values for all timepoints for the comparison. The response rate is the proportion of subjects with a response at the timepoint among the subjects evaluable for bone scan response at the randomization baseline.

Patient bone scan best overall response rate is defined for each comparison as the proportion of subjects having the best bone scan timepoint overall response as R, SD, PD, or UE among subjects with a non-zero BSLA measurement at the randomization baseline. Overall response is judged on all responses observed during the post-baseline period, including unscheduled visits. Responder and SD responses will only be reported if observed prior to PD. No confirmation of R or PD status is required.

Total ALP and PSA Endpoints

Total ALP and PSA endpoints are determined based on the total ALP and PSA laboratory assessments collected as described in the schedule of procedures.

Total ALP response rate is defined as the proportion of subjects with a $\geq 30\%$ reduction of the blood total-ALP level compared to the randomization baseline, confirmed by a second consecutive ALP value 4 or more weeks later but within 9 weeks, among evaluable subjects.

PSA response rate is defined as the proportion of subjects with a $\geq 30\%$ reduction of the blood PSA level, compared to the randomization baseline value, confirmed by a second consecutive PSA value 4 or more weeks later but within 9 weeks, among evaluable subjects.

In addition, **percentage change from randomization baseline in Total ALP** at weeks 12 and 24 will be summarized for Comparison 1.

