Time to total ALP progression is defined as the time (days) from randomization date to the date of first total ALP progression. A progression event is defined as $\geq 25\%$ increase from randomization baseline value, at least 12 weeks from baseline in subjects with no ALP decline from baseline; or $\geq 25\%$ increase above the nadir value, which is confirmed by a second consecutive value obtained 3 or more weeks later but within 9 weeks in subjects with an initial ALP decline from the baseline.

Time to total ALP progression without 12-week restriction is similar to the time to total ALP progression defined above except that 12-week rule is removed in subjects with no ALP decline from baseline.

See [Table 9–4](#) in Appendix [9.1.3](#) for detailed censoring rules.

Time to PSA progression is defined as the time (days) from randomization baseline to the date of first PSA progression. A progression event is defined as $\geq 25\%$ increase from randomization baseline value and an increase in absolute value of ≥ 2 ng/mL, at least 12 weeks from the applicable baseline in subjects with no PSA decline from baseline; or $\geq 25\%$ increase and an absolute increase of ≥ 2 ng/mL above the nadir value, which is confirmed by a second consecutive value obtained 3 or more weeks later but within 9 weeks in subjects with an initial PSA decline from the baseline.

Time to PSA progression without 12 week restriction is similar to the time to PSA progression defined above except that 12-week rule is removed in subjects with no PSA decline from baseline.

See

Table 9–4 in Appendix 9.1.3 for detailed censoring rules .

Analgesic Use and Related Endpoints

Analgesic use in this study will be captured via two methods:

- Analgesic concomitant medication case report form, where the physician records the analgesic medication prescribed to manage pain.
- 24 hour analgesic consumption case report form, in which all analgesic medication taken in the last 24 hours.

Data from both sources will be used to identify strength of each analgesic used by each subject at baseline and post-baseline visits. The amount of medication a subject actually took cannot be calculated due to only prescribed information is collected on the eCRF. Hence, only drug name will be used in identifying non-, weak- or strong- opioids for analgesics related analyses.

Analgesic names will be coded into standard terms using the World Health Organization Drug Dictionary (WHO-DD), Version 2005 Q3.

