Each subject will fill out the complete 11-question BPI-SF using an ePRO device at the Treatment Day 1 visit and at each clinic visit thereafter through Week 48. For subjects in Arm A and Arm B, the modified complete BPI-SF will also be filled out on the day of telephone contacts scheduled for Weeks 28, 32, 40, and 44. The data will be collected for one week (6 days prior to the applicable visit and the morning of the visit) prior to each clinic visit or phone call follow-up.

The BPI-SF (Protocol Section 14.9) is a short, self-administered questionnaire with 11 items, which was designed to evaluate the intensity of, and the impairment caused by pain. All BPI-SF items are scored using rating scales. Four items measure pain intensity (pain now, average pain, worst pain, and least pain) using 0 (“no pain”) to 10 (“pain as bad as you can imagine”) numeric rating scales, and seven items measure the level of interference with function caused by pain (general activity, mood, walking ability, normal work, relations with other people, sleep and enjoyment of life) using 0 (no interference) to 10 (complete interference) rating scales.

The items are aggregated into two dimensions, (1) **Pain severity index**, using the sum of the four items on the pain intensity, and (2) **Function interference index**, using the sum of the seven pain interference items (at least 4 out of 7).

Each BPI-SF subscale, and the two indices for pain severity and function interference, will be summarized using descriptive statistics.

Weekly Average pain score (APS) is defined for each subject at baseline and at each post-baseline date, as the mean of the “average pain score” values in the last 24 hours from the preceding 7 days before each applicable visit or telephone contact per the BPI-SF.

Analysis of Exploratory Endpoints

Identical statistical methods for analyzing time-to-event secondary endpoints, as elucidated in section 6.2.2.2, will be applied to the analysis of time-to-event exploratory endpoints:

- Time to radiological bone progression
- Time to radiological soft-tissue progression
- Time to total alkaline phosphatase (ALP) progression
- Time to ALP progression without 12-week restriction
- Time to PSA progression
- Time to PSA progression without 12-week restriction
- Time to pain progression or increase in analgesic use following baseline
- Time to increase in analgesic use
- Time to increase in physical symptoms of disease based on FPSI-DRS-P

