9.1.3 Censoring rules for other time-to-event endpoints

Comparison 1:

- Arm C subjects who had relevant event assessment or event after ‘pooling cut-off date’ will be censored on last assessment date prior to ‘pooling cut-off date’. Refer to Section 4.5 for pooling cut-off date.
- All other subjects in arms A, B and C, refer to
- [Table 9–4](#) for censoring rules.
- Randomization baseline is used for this comparison
- Time-to-event following randomization = End date - date of randomization +1

Comparison 2:

- Subjects who had a relevant event between date of randomization and Week 24 baseline will be censored at date of Week 24 baseline, with the reason ‘First event occurred between date of randomization and Week 24 baseline’.
- All other subjects refer to
- [Table 9–4](#).
- Week 24 baseline is used for this comparison for following endpoints: Time to first SSE and Time to Pain progression
- Randomization baseline is used for this comparison for exploratory endpoints :Time to ALP progression, time to PSA progression, time to increase in analgesic use and time to pain progression or increase in analgesic use.
- The assessment prior to treatment start is used as baseline for time to increase in physical symptoms of disease.
- Time-to-event following Week 24 baseline = End date - date of week 24 baseline +1.

[Table 9–4](#) applies to the following endpoints:

- **Time to First Symptomatic Skeletal Event**
- **Time to Pain Progression**
- **Time to ALP Progression**
- **Time to ALP Progression without 12-week Restriction**
- **Time to PSA Progression**
- **Time to PSA Progression without 12-week Restriction**
- **Time to Increase in Analgesic Use**
 - Requires Baseline WPS ≤ 7 for inclusion in analysis
- **Time to Pain progression or increase in analgesic use**
 - Requires Baseline WPS ≤ 7 for inclusion in analysis
 - The last assessment for censoring purposes refers to the latest date Pain Progression assessment. The earlier of the date of pain progression or increase in analgesic use is taken as the endpoint.
- **Time to increase in physical symptoms of disease following start of treatment based on FPSI-DRS-P**

Table 9–4 Time-to Event Censoring Rules

Situation	End Date	Censored	Reason for Censoring
No baseline assessment	Relevant Baseline Date	Yes	No baseline assessment.
No post baseline assessment	Relevant Baseline Date	Yes	No post-baseline assessment.
Subject had an event	Date of first event	No	N/A

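### With a 9-week limit on confirming a post-nadir PSA or ALP rise, later rises can count in Arm C but hardly in Arm A if blood is drawn only at clinic visits

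*SAP*

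**What the plan says.** SAP 6.2.3.1.1 (Total ALP and PSA Endpoints) gives progression two branches. Without a decline from baseline, one sufficiently large rise at 12 weeks or later is enough. The other branch applies "in subjects with an initial PSA decline from the baseline" (and likewise for ALP). There, a rise of at least 25% above nadir (for PSA also at least 2 ng/mL) counts only when it meets this condition: "which is confirmed by a second consecutive value obtained 3 or more weeks later but within 9 weeks".

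The SAP does not say when the samples are taken: "Total ALP and PSA endpoints are determined based on the total ALP and PSA laboratory assessments collected as described in the schedule of procedures". SAP 3.2 passes that schedule on: "See Protocol Table 7-1".

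The visit pattern can be partly read from elsewhere. Under BPI Subscales, the questionnaire is completed at clinic visits through Week 48, and for Arms A and B it "will also be filled out on the day of telephone contacts scheduled for Weeks 28, 32, 40, and 44". SAP 1 gives the extended regimen as "Arm C: 12 doses of 50 kBq/kg (55 kBq/kg after implementation of NIST update) radium-223 dichloride every 4 weeks".

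Both endpoints are analysed in Comparison 2. SAP 9.1.3 states: "Randomization baseline is used for this comparison for exploratory endpoints :Time to ALP progression, time to PSA progression". They receive the methods of the secondary time-to-event endpoints, a stratified log-rank test and a stratified Cox model (SAP 6.2.2.2). A subject without a qualifying event is censored at the last assessment before database cutoff (Table 9-4).

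**The concern.** An upper limit on the confirmation interval works only if consecutive samples are closer together than the limit. Here the limit is the same for every arm, but the apparent visit spacing after Week 24 is not. A lasting PSA rise that begins at Week 30 could be confirmed in Arm C at the next 4-weekly visit. In Arm A it would be seen at Week 36 and again at Week 48, too late to confirm it, and the subject would be censored as progression-free.

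The loss has a direction. Comparison 2 sets Arm A against Arm C, so events missing from Arm A make the extended regimen look worse on both markers through visit frequency alone. SAP 6.2 recognises this kind of problem for imaging: it drops the Week 24 re-baseline because incomplete assessments could favour one arm. The other confirmation rules in the SAP (bone scan, pain improvement, FPSI-DRS-P) set a minimum interval only. The 9-week ceiling appears only in the PSA and ALP definitions.

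**Working it through.** **Plan's own figure.** The SAP gives no number for PSA or ALP confirmation under the visit schedule. Its only 12-week interval arithmetic is the imaging rule under Table 9-5: 2 × (12 + 2) = 28 weeks, which reproduces. It uses a ±2-week window, stated for tumor assessments and not for laboratory samples.

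**Inputs.**
- Confirmation window: 3 to 9 weeks, next consecutive value (SAP 6.2.3.1.1).
- Arms A and B: telephone contacts at Weeks 28, 32, 40 and 44, hence clinic visits near Weeks 24, 36 and 48 (inference).
- Arm C: dosing every 4 weeks. Dose 7 falls at 6 × 4 = Week 24 and dose 12 at 11 × 4 = Week 44 if undelayed.
- Assumption: PSA and ALP are drawn at clinic visits.
- Assumption: each visit deviates uniformly within ±w weeks, with w from 0 to 3.

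**Nominal gaps in Arm A.** 36 − 24 = 12 and 48 − 36 = 12 weeks, both above 9. From the end-of-treatment visit (30 ± 7 days after the last dose, SAP 4.5.1) following a Week 20 dose, the gap to Week 36 averages 36 − (20 + 30/7) = 11.7 weeks. It is 9 weeks or less in 0% of cases with w = 0 or 1 at the Week 36 visit, and in 0.5% with w = 2.

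**Gaps with visit windows.** The gap is g + T, where T is the difference of two independent uniform deviations. For 0 ≤ a ≤ 2w, P(T ≤ −a) = (2w − a)²/(8w²).
- For g = 12, the pair qualifies if T ≤ −3. With w = 2: (4 − 3)²/32 = 1/32 = 3.1%. With w = 3: (6 − 3)²/72 = 9/72 = 12.5%. With w = 0 or 1, T cannot reach −3.
- For g = 4, the pair fails if T < −1 or T > 5. With w = 1: 1 − 1/8 = 87.5%. With w = 2: 1 − 9/32 = 71.9%. With w = 3: 1 − 25/72 − 1/72 = 63.9%.

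| Visit window | 12-week spacing: pairs within 3–9 weeks | 4-week spacing: pairs within 3–9 weeks |
|---|---|---|
| 0 | 0% | 100% |
| ±1 week | 0% | 87.5% |
| ±2 weeks | 3.1% | 71.9% |
| ±3 weeks | 12.5% | 63.9% |

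**Illustration.** Take a lasting rise with onset uniform over Weeks 24 to 48 and no visit deviation. On visits at Weeks 24, 36 and 48, none can be confirmed by Week 48. On 4-weekly visits, any rise with onset by Week 44 can be: (44 − 24)/24 = 83%. With 4-weekly laboratory samples in Arm A as well, the difference disappears.

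**Earlier rises.** A rise first seen at Week 20 can be confirmed at Week 24 in every arm. The problem starts with rises first seen at about Week 24.

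**Comparison 1.** Arms A and B share the contact schedule. Arm C data stop counting at the pooling cut-off, the 7th dose date for those who receive it (SAP 4.5.2, 9.1.3). Late events are therefore lost on both sides of the comparison.

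**The case against.** The strongest objection is that the deciding fact is missing. The text on telephone contacts concerns a pain questionnaire. It says nothing about blood draws, local laboratories or unscheduled samples, and nothing about visits after Week 48. Sampling at every Arm C dose is likewise assumed. This stands, and it makes the point conditional on Protocol Table 7-1.

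Other limits also stand. Subjects without an initial decline need no confirmation, so their progressions are unaffected. Dose delays, which SAP 5 acknowledges, could move an Arm A end-of-treatment visit to about Week 28. That is 36 − 28 = 8 weeks before a Week 36 visit and inside the limit, if follow-up weeks count from treatment start, which the SAP does not say. Arm C subjects who stop dosing early lose the closer spacing. The definition was chosen deliberately, to match the compound standard (Table 7-1 of the SAP). The endpoints are exploratory.

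A reader might go further and infer that progression is almost unconfirmable in Arms A and B throughout, or that the arms would differ by some 30% against 99% confirmed by Week 48, as one simulation of identical marker courses gave. The documents do not support either reading. Rises repeated by about Week 24 can be confirmed in all arms. The simulation assumes that every subject declines by 20–70% and uses nadir times, doubling times and assay noise that the SAP does not contain. If half the subjects decline, and detection is similar in the rest, the 69-point gap falls to about 35 points; at a quarter, to about 17.

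None of this removes the mismatch between the limit and a 12-week spacing, or its direction.

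**Conclusion.** The concern holds conditionally. If Arm A has PSA and ALP samples only at 12-weekly clinic visits after Week 24, at most about 13% of consecutive pairs fall within the 9-week limit even with ±3-week windows, and none do with windows up to ±1 week. Most Arm A rises first seen from about Week 24 in subjects with an initial decline are then censored as event-free, while the same rises in Arm C can count until about Weeks 44 to 48. The exploratory Comparison 2 analyses of both endpoints are biased against the extended regimen. How far the hazard ratio moves cannot be fixed from the SAP. It depends on the share of subjects who decline, the timing of nadirs, dose delays, unscheduled samples and early stopping in Arm C.

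Two wider inferences fail. Comparison 1 has no clear between-arm bias, only lost late events. The co-primary and secondary results do not use this definition.

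**What to change.** First, check the 9-week limit against the laboratory schedule in Protocol Table 7-1. If Arm A is sampled at intervals of 9 weeks or less after Week 24, a sentence in the SAP saying so closes the point.

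If sampling there is 12-weekly:
1. In the PSA and ALP progression definitions, let the next scheduled assessment at least 3 weeks later confirm the rise, with the upper limit set to the scheduled laboratory interval plus its window. That would be 12 + 2 = 14 weeks if the imaging interval and window also apply to laboratory samples, which the SAP does not state.
2. For Comparison 2, add an analysis that after Week 24 uses only laboratory timepoints scheduled in both arms. A wider limit alone still leaves Arm C observed more often, so its rises would be detected sooner.
3. Report the 9-week compound-standard definition alongside.

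The cost is SAP wording and a derivation change on samples the trial already collects. The downsides are a departure from the compound standard, softened by item 3, and some Arm C samples left unused in item 2. The PSA and ALP response definitions carry the same 9-week ceiling and can be checked at the same time.

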Simulations assume continuous event and censoring times. Last treatment is assumed to occur 44 weeks (10.12 months) after last subject accrued.

Primary endpoint power calculations were based on simulations programmed using SAS version 9.2 and used 10,000 replicates.

The simulations, taking into account the correlated nature of the data supporting the two comparisons in this study design, indicated that the proportion of replicates rejecting at least one null hypothesis was 16.4%, and the proportion of replicates rejecting both was 2.3%.

4. General Statistical Considerations

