- The first bone scan with ≥ 2 new lesions compared to baseline is observed < 12 weeks from randomization and is confirmed by a second bone scan taken ≥ 6 weeks later showing ≥ 2 additional new lesions (a total of ≥ 4 new lesions compared to baseline); or
- The first bone scan with ≥ 2 new lesions compared to baseline is observed ≥ 12 weeks from randomization and the new lesions are verified on the next bone scan ≥ 6 weeks later (a total of ≥ 2 new lesions compared to baseline).

The date of progression of bone disease will be the date of the first observed bone progression, not the date that confirmed the bone progression.

The date of radiological progression will be determined following the rules in [Table 9–6](#).

Radiological progression-free survival is defined for each comparison as the time (days) from the randomization baseline to the date of radiological disease progression or death from any cause (if death occurs without prior progression). See [Table 9–7](#) in Appendix 9.1.5 for detailed censoring rules for both Comparison 1 and Comparison 2.

If data permits, unconfirmed radiological progression-free survival and time to unconfirmed radiological progression will be analyzed as sensitivity analyses based on central reviewer. Bone progression in this case does not require confirmation.

Pain endpoints

The pain data collected from ePRO will be used for these analyses.

Worst pain score (WPS) at a given visit is defined for each subject as the mean of the 7 day “worst pain score” assessments taken on or before each applicable visit. If less than 4 non-

missing WPS values are available for a given visit, then the weekly worst pain score will be left missing for that visit.

Timepoint pain improvement rate is defined with respect to each applicable baseline as the proportion of subjects with a 30% and 2-point decrease in WPS with respect to the applicable baseline assessment over 2 consecutive assessment periods conducted at least 3 weeks apart among subjects with a WPS score ≥ 4 at the applicable baseline. The first of the 2 consecutive periods is taken to be the date of improvement.

Time to pain progression is defined for each comparison in subjects with a WPS of ≤ 7 at the applicable baseline as the time from the applicable start date to an increase of 2 or more points in WPS (with respect to the applicable baseline). Refer to

Table 9–4 in Appendix 9.1.3 for detailed censoring rules.

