Each standardized analgesic name will be classified by strength type as non-opioid, weak opioid, or strong opioid.

An increase in analgesic use following randomization baseline is defined in Table 6–3 below. If a subject is using more than one type of analgesic, the strongest type will be used in the analysis.

Table 6–3 Increase in Analgesic Use Algorithm

Baseline intake	Post baseline
No analgesics or a non-opioid	Initiation of any opioid
Weak opioid	Initiation of any strong opioid or adding an additional weak opioid
Strong opioid	Initiation of an additional strong opioid

Pain improvement rate without increase in analgesic use following baseline is defined at each post-baseline assessment time point as the proportion of subjects with a 30% and 2-point decrease in average WPS over 2 consecutive assessment periods conducted at least 4 weeks apart, without a corresponding increase in analgesic use over those 2 periods. The denominator is the number of subjects with a non-missing WPS of at least 4 at randomization.

Time to increase in analgesic use is defined as the time in days from randomization baseline until the first increase in analgesic use for subjects with baseline average WPS of ≤ 7 and non-missing baseline assessment of analgesic use. See Table 9–5 in Appendix 9.1.4 for detailed censoring rules.

Pain progression or increase in analgesic use following baseline is defined as the time in days from randomization baseline until the earlier of pain progression or a first increase in analgesic use for subjects with a non-missing baseline average WPS of ≤ 7 . See [Table 9–4](#) in [Appendix 9.1.3](#) for detailed censoring rules.

Change in analgesic use following baseline : A shift table will be presented to summarize the change in strength of analgesic use from randomization baseline to the strongest use at post-baseline. The strength type will include: no analgesics or non-opioid, weak opioid, and strong opioid.

NCCN-FACT FPSI-17 Endpoints

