The NCCN-FACT FPSI-17 is a validated instrument that was developed to assess symptoms of prostate cancer, symptoms caused by the treatment of prostate cancer, and the health related quality of life of prostate cancer patients. [12] The instrument contains 17 items, each of which utilizes a Likert scale with 5 possible responses. Ten items reflect disease related physical symptoms of disease and the responses on the items are to be summed to calculate a disease related physical symptom subscale score (FPSI-DRS-P, Disease Related Symptoms – Physical), One item represents emotional symptoms of disease and the response to that item is used to calculate a disease related emotional symptom subscale score (FPSI-DRS-E, Disease Related Symptoms – Emotional). Four items represent treatment related symptoms and the responses to these items are summed to calculate a treatment side effect subscale score (FPSI-TSE, Treatment Side Effects). Finally, two items represent functional well-being and the responses to those items are summed to calculate a functional/well-being subscale score (FPSI-F/WB, Function/Well Being).

The NCCN-FACT FPSI-17 total score and each of its subscale scores, FPSI-DRS-P, FPSI-DRS-E, FPSI-TSE, and FPSI-F/WB, will be summarized by visit.

Time to increase in physical symptoms of disease based on FPSI-DRS-P will be evaluated based on the FPSI-DRS-P subscale score of the NCCN-FACT, as the time from treatment start to the first increase in physical symptoms of disease on-study. NCCN-FACT FPSI-17 was not collected prior to randomization, so baseline is the assessment collected prior to first dosing. An increase is defined as a 2 point drop in DRS-P score that persists for two consecutive assessments at least 4 weeks apart, if two consecutive assessment are available. If there is a 2 point drop in the DRS-P score and the next assessment is not available due to death then that single 2 point drop would count as a deterioration. See [Table 9–4](#) in [Appendix 9.1.3](#) for detailed censoring rules.

BPI Subscales

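### Pain improvement without analgesic increase needs periods 4 weeks apart on a 28-day cycle, while the secondary pain improvement rate needs only 3 weeks

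*SAP*

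**What the plan says.** Two endpoints in the SAP share one pain criterion.

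- **Secondary (6.2.2.1, Pain endpoints).** The timepoint pain improvement rate needs a 30% and 2-point fall in worst pain score (WPS) "over 2 consecutive assessment periods conducted at least 3 weeks apart", among subjects with WPS of at least 4 at the applicable baseline.
- **Exploratory (6.2.3.1.1, Analgesic Use and Related Endpoints).** The rate without increase in analgesic use needs a "30% and 2-point decrease in average WPS over 2 consecutive assessment periods conducted at least 4 weeks apart", with no corresponding analgesic increase, among subjects with WPS of at least 4 at randomization. Section 6.2.3.1 lists it at Week 12, Week 24, end of treatment (EOT) and overall. The analysis section summarizes it with exact intervals and plots it by timepoint.

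The visit cycle is 4-weekly. Section 1 gives each arm "radium-223 dichloride every 4 weeks", and 6.2.3.1.1 (BPI Subscales) collects the pain questionnaire at each clinic visit through Week 48. Arms A and B also have telephone contacts at Weeks 28, 32, 40 and 44. Each collection period covers 7 days ending on the visit day. The only clinic-visit window stated in days is in 4.5.1: for Arm A, the EOT visit falls 30±7 days after the last dose.

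Three other exploratory definitions also carry a 4-week minimum:

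- ALP response: "confirmed by a second consecutive ALP value 4 or more weeks later but within 9 weeks"
- PSA response: "confirmed by a second consecutive PSA value 4 or more weeks later but within 9 weeks"
- FPSI-DRS-P deterioration: "a 2 point drop in DRS-P score that persists for two consecutive assessments at least 4 weeks apart, if two consecutive assessment are available"

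**The concern.** A minimum spacing equal to the planned spacing leaves no room for a visit that closes the gap by a day. The subject improved at both periods, but the pair does not count. Because the rate is reported by timepoint, a short gap removes that subject's success at that timepoint, and a good pair elsewhere does not restore it.

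The second consequence is for reading the results. The exploratory rate exists to show how much of the pain improvement remains once analgesic increase is excluded. A reader who sets it beside the secondary rate will attribute the difference to analgesics. As written, part of that difference can come from visit dates alone.

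**Working it through.** **1. Nominal spacing.** Section 3.4 states: "Last treatment is assumed to occur 44 weeks (10.12 months) after last subject accrued". Twelve doses make 11 intervals: 11 × 28 = 308 days = 44 weeks, and 308 / 30.4375 = 10.12 months. The plan's own figure is reproduced, so the nominal gap is exactly 28 days. The margin over a 4-week minimum is 28 − 28 = 0 days; over a 3-week minimum it is 28 − 21 = 7 days.

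**2. EOT visit, from the SAP's own window.** 30 ± 7 gives days 23 to 37, which is 15 permitted days. If the last-dose visit is the previous assessment:

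- 4-week minimum: days 23 to 27 fail, 5 of 15 days.
- 3-week minimum: none fail, since the earliest permitted day is 23.

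This counts permitted days. It does not predict how often visits fall on them.

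**3. The 4-weekly visits, under an assumption.** The SAP gives no window for these, so assume each visit deviates from a fixed calendar by a whole number of days, uniform on ±w and independent. A pair is short when the second deviation is smaller than the first:

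P(gap < 28) = w / (2w + 1)

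| Assumed window | Gap under 28 days | Gap under 21 days |
|---|---|---|
| ±1 day | 1/3 = 33% | 0% |
| ±2 days | 2/5 = 40% | 0% |
| ±3 days | 3/7 = 43% | 0% |
| ±7 days | 7/15 = 47% | 28/225 = 12.4% |

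The last entry counts differences of 8 to 14 days: 7+6+5+4+3+2+1 = 28 of 15² = 225 pairs. If each visit is instead scheduled from the previous one, the 28-day column is unchanged and the 21-day column is 0% throughout.

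**4. Effect on a timepoint rate.** If a share f of the relevant pairs is short, independently of outcome, the observed rate is the true rate × (1 − f). For an illustrative true rate of 30%:

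- f = 10%: 0.30 × 0.90 = 27%
- f = 40%: 0.30 × 0.60 = 18%

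**5. How the interval is counted.** Neither definition says between which dates the periods are separated. Counted from the end of one 7-day period to the start of the next, the on-schedule gap is 28 − 6 = 22 days. That meets 3 weeks but never 4.

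**6. Endpoints that any pair can satisfy.** For a response lasting n visits, the chance that no consecutive pair reaches 28 days is C(2w+1, n) / (2w+1)ⁿ on a fixed calendar, or (w/(2w+1))ⁿ⁻¹ if visits are scheduled from the previous one.

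| Visits in response | ±3 days: fixed / from previous | ±7 days: fixed / from previous |
|---|---|---|
| 2 | 43% / 43% | 47% / 47% |
| 3 | 35/343 = 10.2% / 18.4% | 455/3375 = 13.5% / 21.8% |
| 4 | 35/2401 = 1.5% / 7.9% | 1365/50625 = 2.7% / 10.2% |

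The loss falls quickly once the response lasts beyond two visits.

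**The case against.** **The wider reading.** A reader might infer that all four definitions with a 4-week minimum are defective and that any visit a day early voids a true result. The SAP does not support this, for four reasons.

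- What counts is the gap between visits. An early visit after an equally early one still passes.
- ALP and PSA response have no fixed timepoint, so a later pair can qualify. An FPSI-DRS-P event can likewise come from a later pair, though probably with a later date. The FPSI-DRS-P wording also leaves open how a pair closer than 4 weeks is handled.
- A 28-day spacing is documented for dosing and largely for the pain questionnaire. ALP and PSA sampling is left to the protocol's schedule, and the SAP gives no FPSI-17 schedule.
- For ALP response the rule is deliberate. Table 7–1 of the SAP adopts the compound standard, with 3 weeks for progression and 4 weeks for response in adjacent rows. The progression rule is therefore no evidence of a slip in the response rule.

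**Against the narrower point.** No formal contrast between the two pain rates is planned; both are descriptive. They already differ for Comparison 2, where one uses the applicable baseline and the other randomization. The exploratory endpoint's overall rate need not depend on one particular pair. Dose delays lengthen some gaps, so symmetric scatter may overstate the loss. The rule is the same in every arm, and no differential bias is shown.

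All of this stands. It limits the scope and weight of the point, but does not explain why one pain criterion carries two spacing rules.

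**Conclusion.** The point holds for the exploratory pain improvement rate without increase in analgesic use. Its spacing rule conflicts, without explanation, with that of the secondary rate built on the same criterion, and it equals the nominal visit interval. Two results need no assumption about scatter: the margin is zero days, and 5 of the 15 permitted EOT days fail when the last-dose visit is the previous assessment.

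The 33% to 47% of short pairs, against 0% to 12% with a 21-day minimum, rests on assumed windows of ±1 to ±7 days and is a range, not an estimate for this trial.

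Severity is minor. The endpoint is exploratory and descriptive, and the primary and secondary analyses are unaffected. ALP response should not be counted as an error. For PSA response and FPSI-DRS-P the question cannot be settled from the SAP alone.

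**What to change.** - In 6.2.3.1.1, change the minimum spacing for pain improvement without increase in analgesic use from 4 weeks to 3, matching 6.2.2.1.
- In both pain definitions, state that the interval is counted between visit dates (or telephone-contact dates).
- For PSA response and FPSI-DRS-P, check the protocol's schedule and visit windows. If assessments are 4-weekly, state a tolerance in days; otherwise leave the definitions alone.
- Leave ALP response at the stated compound standard.

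The cost is one changed number, one clarifying sentence and the matching derivation code. The trade-off is that slightly shorter persistence of pain improvement is accepted, as the secondary endpoint already accepts it.
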